***Exclusion Criteria for Participants with MDD:***

1. Current alcohol and/or substance use disorder as confirmed by the M.I.N.I 5.0.
2. Presence of comorbid psychiatric disorder other than MDD that is a focus of clinical concern as confirmed by the M.I.N.I 5.0.
3. Medications approved and/or employed off-label for cognitive dysfunction

(e.g., psychostimulants).

4. Any medication for a general medical disorder that, in the opinion of the investigator, may affect cognitive function.
5. Use of benzodiazepines within 12 hours of cognitive assessments.
6. Consumption of alcohol within 8 hours of cognitive assessments.7 . Inconsistent use or abuse of marijuana.
8. Physical, cognitive, or language impairments sufficient to adversely affect data derived from cognitive assessments.
9. Diagnosed reading disability or dyslexia.
10. Clinically significant learning disorder by history.
11. Electroconvulsive therapy (ECT) in the last 6 months.
12. History of moderate or severe head trauma (e.g., loss of consciousness for >1 hour), other neurological disorders, or unstable systemic medical diseases that in the opinion of the investigator are likely to affect the central nervous system.
13. Pregnant and/or breastfeeding.
14. Received investigational agents as part of a separate study within 30 days of the screening visit.
15. Actively suicidal/presence of suicidal ideation or evaluated as being a suicide risk (as per clinical judgment using the Columbia-Suicide Severity Rating Scale).
16. Currently receiving treatment with Monoamine Oxidase Inhibitors (MAOIs) anti-depressants, antibiotics such as linezolid, or intravenous methylene blue.
17. Previous hypersensitivity reaction to vortioxetine or any components of the formulation.  
Angioedema has been reported in patients treated with vortioxetine.
18. Clinical worsening symptoms of depression and suicide risk – in both adult and pediatric age groups.
19. Serotonin syndrome
20. Abnormal bleeding

21. Previous history of mania/hypomania
22. Angle closure glaucoma
23. Hyponatremia
24. Moderate hepatic impairment
25. History of seizures and epilepsy

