## **Transition to Enrollment**

Patient will discontinue only antidepressants. Patients' existing antidepressant dosage will be decreased gradually over a course 10-14 days. At the same time, participants will be started on 10mg of Vortioxetine. It takes about 10-14 days for Vortioxetine to achieve steady states. For patients who are already taking antidepressants at the start of study, if they are abruptly discontinued, they are at risk for discontinuation syndrome. Therefore, both drugs will be co-prescribed for about 10-14 days and then the index antidepressant will be discontinued.

Serotonin syndrome or other additive side effects is very unlikely to be a concern. Should the patient's physician determine another optimal schedule, this will be followed instead. All MDD participants will be supervised by [name], prior to enrollment of the study. All patients will be monitored by a psychiatrist during the study. Furthermore, patients will have access to a 24-hour study number where they can contact research staff anytime, should they experience any adverse events. Therefore, there will always be an open line of communication between patients and the research staff.

The above mentioned procedures will only be carried out once participants have consented to take part in the research and signed the informed consent form.

Patients will be seen by a clinician on a biweekly basis for the antidepressant washout period. Clinician will be assessing the patient on adverse side effects, as well as mood.

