### ***Visit 2 (Day 0: Week 0; Baseline)***

Participant will be asked to report any adverse event(s) or any changes to medications. The Clinical Global Impression – Severity (CGI-S), MADRS, as well as the CSSRS scales will be used as part of participant assessment. Anthropometrics (including weight and waist circumference), resting heart rate and blood pressure will be measured. History of caffeine, alcohol, nicotine, exercise and marijuana use will be recorded as well. Participants will be provided with an opportunity to work through the modified THINC-it to minimize potential practice effects with a research team member. This will allow the participant with an opportunity to ask any outstanding questions. The THINC-it tool will be administered via tablet to evaluate objective and subjective measures of cognitive function. THINC-it tests will be consistently delivered in the following order: Spotter, Symbol Check, Codebreaker, Trails, and PDQ-5-D to all participants with a member of the research team instructing participants to read the tutorial

instructions preceding each of the THINC-it tasks. Participants will complete the pen-and-paper version of the Digit Symbol Substitution Test (DSST) and the Trail Making Test B (TMT-B).

Participants will also complete all secondary self-report assessments using paper-based scales/questionnaires and consist of the following scales: Endicott Workplace Productivity Scale (EWPS), Sheehan Disability Scale (SDS), Wellbeing Index (WHO-5), Snaith-Hamilton Pleasure Scale (SHAPS), Generalized Anxiety Disorder (GAD-7), Perceived Deficits Questionnaire for Depression (PDQ-5-D), International Physical Activity Questionnaire (IPAQ), 36-Item Short Form Survey Instrument (SF-36), Insomnia Severity Index (ISI), Pittsburgh Sleep Quality Index (PSQI), Epworth Sleepiness Scale (ESS) and THINC-it satisfaction questionnaire. All self reports will be administered by a member. All study procedures will take place in a quiet setting. Fasting (12-hours) clinical and research bloodwork will also be collected.

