### **MDD PATIENT SUMMARY CHART**

Visit	Screening (Visit 1)	Week 0 (Baseline, Visit 2)	Week 2 (Visit 3)	Week 4 (Visit 4)	Week 8 (Endpoint, Visit 5)	Post-Study two weeks clinical visit for drug discontinuation. Additional visits will be scheduled as needed.
Consent	X					
Physician visit		X	X	X	X	X
Bloodwork		X			X	
Demographics	X					
Inclusion/ exclusion	X					
Adverse events	X	X	X	X	X	
Current Medications	X					
Medication Changes		X	X	X	X	
M.I.N.I 5.0	X					
SCID	X					
Psychiatric/Medical History	X					
Anthropometrics	X	X	X	X	X	
Lifestyle Factors	X	X	X	X	X	
Montgomery Åsberg Depression Rating Scale (MADRS) > 20	X	X	X	X	X	
THINC-it Practice		X				
THINC-it Cognitive test		X	X		X	
CSSRS	X	X	X	X	X	
DSST (pen/paper)		X	X		X	
TMT-B (pen/paper)		X	X		X	
NART	X					
CGI-I/CGI-S		X	X	X	X	
International Physical Activity Questionnaire (IPAQ)		X		X	X	
Vortioxetine Treatment		X	X	X		
Dispensing medication		X	X	X		
Effort Expenditure for Rewards Task (EEfRT) – optional					X	

Endicott Workplace Productivity Scale (EWPS)		X	X		X	
Sheehan Disability Scale (SDS)		X	X		X	
Wellbeing Index (WHO-5)		X	X		X	
Snaith-Hamilton Pleasure Scale Questionnaire (SHAPS)		X	X		X	
Generalized Anxiety Disorder (GAD-7)		X	X		X	
Perceived Deficits Questionnaire for Depression (PDQ-5-D)		X	X		X	
36-Item Short Form Survey Instrument (SF-36)		X	X		X	
Insomnia Severity Index (ISI)		X	X		X	
Pittsburgh Sleep Quality Index (PSQI)		X	X		X	
Epworth Sleepiness Scale (ESS)		X	X		X	
THINC-it satisfaction questionnaire		X				

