## **Side effects**

Most Common:

- Gastrointestinal adverse events; including nausea, vomiting, constipation/diarrhea. Highest incidence occurs during the first week of treatment. 21-32%
- Sexual dysfunction 14-34%

Less Common: 1-10%

- Dry mouth
- Dyspepsia (discomfort of the abdomen)
- Dizziness
- Somnolence/sedation
- Fatigue
- Insomnia
- Abnormal dreams
- Hyperhidrosis (increase sweating)
- Arthralgia (joint pain)
- Decreased appetite

Rare: %10>

- Nervous system disorders
  - Skin and subcutaneous tissue disorders
  - Psychiatric disorders
- 
- Serotonin Syndrome has been reported with serotonergic anti-depressants (SSRIs, SNRIs, and others), including with Vortioxetine both when taken alone, but especially when coadministered with other serotonergic agents (including triptans, tricyclic antidepressants, fentanyl, lithium, tramadol, tryptophan, buspirone, and St. John's Wort).
  - Treatment with serotonergic antidepressants (SSRIs, SNRIs, and others) may increase the risk of abnormal bleeding. Patients should be cautioned about the increased risk of bleeding when Vortioxetine is coadministered with nonsteroidal anti-inflammatory drugs (NSAIDs), aspirin, or other drugs that affect coagulation.
  - Activation of Mania/Hypomania can occur with antidepressant treatment.
  - Angle Closure Glaucoma: Angle closure glaucoma has occurred in patients with untreated anatomically narrow angles treated with antidepressants.
  - Hyponatremia can occur in association with the syndrome of inappropriate antidiuretic hormone secretion (SIADH).

Please see product monograph for full details.

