## Contraindications

Hypersensitivity to vortioxetine or any components of the formulation. Angioedema has been reported in patients treated with vortioxetine. The use of monoamine oxidase inhibitors (MAOI) intended to treat psychiatric disorders with vortioxetine or within 21 days of stopping treatment with vortioxetine is contraindicated because of an increased risk of serotonin syndrome. The use of vortioxetine within 14 days of stopping an MAOI intended to treat psychiatric disorders is also contraindicated.

Starting vortioxetine in a patient who is being treated with MAOIs such as linezolid or intravenous methylene blue is also contraindicated because of an increased risk of serotonin

syndrome.

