## **CONDITIONS FOR WITHDRAWAL FROM THE STUDY**

Participants may discontinue from the study treatment and assessments at any time. Specific reasons for discontinuing a participant from this study are:

1. Voluntary discontinuation by the participant at any time without prejudice to further treatment.
2. Non-compliance to the protocol as judged by the investigator.
3. Participant becomes pregnant.
4. Increased risk of suicide ideation.
5. Any adverse event that, in the opinion of an investigator, puts the subject at risk.

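### Exclusion item 24 bars moderate hepatic impairment only; as written, no rule excludes stable severe impairment

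*Combined protocol and SAP*

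**What the plan says.** The only hepatic rule is item 24 of the exclusion criteria for participants with MDD, which consists of three words: "Moderate hepatic impairment". The closest general medical exclusion is the last part of item 12, which covers "unstable systemic medical diseases that in the opinion of the investigator are likely to affect the central nervous system".

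Other parts of the document bear on the point without stating a hepatic rule:

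- Contraindications opens with "Hypersensitivity to vortioxetine or any components of the formulation" and goes on to MAO inhibitors. It has no hepatic entry.
- The side-effects section closes with "Please see product monograph for full details".
- Transition to Enrollment provides for supervision of MDD participants before they are enrolled and adds that "All patients will be monitored by a psychiatrist during the study".
- Visit 2 (Baseline) states that "Fasting (12-hours) clinical and research bloodwork will also be collected". No liver threshold or eligibility action is attached to it.

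**The concern.** An exclusion graded by severity should bar the named grade and everything worse. Item 24 bars one grade and says nothing of the next. Followed exactly, it turns away a candidate with moderate impairment and gives no ground for turning away one with stable severe impairment.

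What is at stake is patient safety at entry. The item stands in a run of drug-safety exclusions, several of which reappear as warnings in the side-effects section, so its purpose is evidently to protect patients from the study drug. A rule of that kind should give the right answer from its own words, without the reader supplying the missing grade. The analysis is not at stake.

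**Working it through.** No arithmetic applies beyond counting. The check is whether any written rule, read as it stands, excludes a patient with stable severe hepatic impairment.

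**Step 1: where the liver is mentioned.** In the whole document *hepatic* occurs once (item 24) and *liver* as a word occurs once (Adverse Events, as an example of a clinical sign). Rules naming severe hepatic impairment: 0. MDD exclusion items naming the liver: 1 of 25, with one grade given.

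**Step 2: how the same list handles grades elsewhere.** Item 12, on head trauma, names both the moderate and the severe grade. A reader therefore cannot assume that *moderate* alone is this list's shorthand for moderate and above.

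**Step 3: whether another rule covers the case.**

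| Place | What it reaches | Excludes stable severe impairment as such? |
|---|---|---|
| Exclusion item 4 | Medication that may affect cognition | No |
| Exclusion item 8 | Impairments that distort cognitive test data | No |
| Exclusion item 12 | Systemic disease, if unstable and judged likely to affect the central nervous system | No |
| Exclusion items 20 and 23 | Abnormal bleeding; hyponatremia | No, though either may catch a patient with that complication |
| Eligibility Criteria, case-by-case review | Interactions with current medication; effect on study results | No |
| Study Medication (dosing) | 10 or 20 mg/day; no hepatic adjustment | No |
| Contraindications | Hypersensitivity; MAO inhibitors | No |
| Side effects, pointer to the monograph | General reference; sets no entry rule | No |
| Baseline bloodwork | Collected with no liver threshold | No |
| Conditions for Withdrawal, item 5: "Any adverse event that, in the opinion of an investigator, puts the subject at risk" | Acts only after enrolment | No |

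**Step 4: who applies the list, and when.** Under Visit 1 (Screening), a research team member assesses eligibility against the criteria. The MDD Patient Summary Chart places the inclusion/exclusion check at screening and first marks a physician visit at Week 0. The same chart marks both the first bloodwork and the first "Dispensing medication" at Week 0. The person applying item 24 is not stated to be a physician, and no laboratory result is scheduled before that check.

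**Result.** No written rule excludes the case. The gap follows from the ordering of the grades alone: whatever reason justified excluding the moderate grade applies at least as strongly to the severe one.

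**The case against.** The strongest reply is that nobody would enrol such a patient. Items 18 to 25 are mostly bare fragments without grade, time frame or threshold, meant to be applied with clinical sense, and in that setting *moderate* reads naturally as a floor. Item 12 is a fully drafted sentence, so its fuller wording is weak evidence about a fragment. Absence from an exclusion list does not oblige anyone to enrol. Candidates give a medical history, are supervised before enrolment, see a physician at Week 0 and are monitored by a psychiatrist. Some severe cases would also be caught by items 8, 12, 20 or 23. On this view the point is editorial.

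Much of this stands. The intended meaning is hardly in doubt, and the practical route to harm is narrow. The documents do not describe how the drug behaves in hepatic impairment, so the risk to a patient who did slip through cannot be sized from them.

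The reply does not supply a written rule that covers the case. General supervision is not an eligibility criterion, and the items that might catch some patients do so through complications or judgement. The wording of a safety exclusion is what the screener works from, so it should be correct on its face.

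**Conclusion.** The concern holds. As worded, item 24 excludes the lesser grade of hepatic impairment and leaves stable severe impairment eligible, with nothing else in the document to exclude it. It should be corrected.

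The size is small: 1 of 25 exclusion items, applying to all candidates for 100 MDD places, with few patients and possibly none likely to be affected. That last statement is a judgement based on the outpatient psychiatric setting and the general safeguards, because no frequency of hepatic impairment is given. Power, alpha, sample size and the primary conclusion are untouched.

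The conclusion rests on two things: a literal reading of the criterion, and the premise that a safety exclusion at one grade should extend to the worse grade. It makes no claim about the drug's pharmacology.

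**What to change.** Amend item 24 to read *Moderate or severe hepatic impairment*, and check the grade against the product monograph cited under Side effects. This matches the form already used for head trauma in item 12.

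The cost is two words in the next protocol amendment, with no effect on sample size, data collection or analysis.

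Reviewing the baseline bloodwork before the first dispensing is a separate, optional step and is not needed to close this gap. If the sponsor wanted it, either the draw would have to move ahead of Week 0 or dispensing would have to wait for the results.

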***Inclusion Criteria for Healthy Controls:***

1. No current or past history of mental disorder as evidenced by the M.I.N.I. 5.0 for DSM-IV.
2. No first-degree relative with an established diagnosis by a healthcare provider of a mood or psychiatric disorder.
3. No unstable medical disorders.

***Exclusion Criteria for Healthy Controls:***

1. Use of any medication for a general medical disorder and/or condition that, in the opinion of the investigator, may affect cognitive function (e.g., corticosteroids, beta-blockers).
2. Pregnant and/or breastfeeding.
3. Consumption of alcohol within 8 hours of THINC-it tool administration.
4. Inconsistent use or abuse of marijuana.

## **Transition to Enrollment**

Patient will discontinue only antidepressants. Patients' existing antidepressant dosage will be decreased gradually over a course 10-14 days. At the same time, participants will be started on 10mg of Vortioxetine. It takes about 10-14 days for Vortioxetine to achieve steady states. For patients who are already taking antidepressants at the start of study, if they are abruptly discontinued, they are at risk for discontinuation syndrome. Therefore, both drugs will be co-prescribed for about 10-14 days and then the index antidepressant will be discontinued.

Serotonin syndrome or other additive side effects is very unlikely to be a concern. Should the patient's physician determine another optimal schedule, this will be followed instead. All MDD participants will be supervised by [name], prior to enrollment of the study. All patients will be monitored by a psychiatrist during the study. Furthermore, patients will have access to a 24-hour study number where they can contact research staff anytime, should they experience any adverse events. Therefore, there will always be an open line of communication between patients and the research staff.

The above mentioned procedures will only be carried out once participants have consented to take part in the research and signed the informed consent form.

Patients will be seen by a clinician on a biweekly basis for the antidepressant washout period. Clinician will be assessing the patient on adverse side effects, as well as mood.

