## ELIGIBILITY CRITERIA

The eligibility criteria provided below do not unnecessarily filter and/or restrict select patients.

The overarching aim of enrollment is to include representative patients to enhance the ecological validity of our results with careful consideration surrounding those patients likely to evince impairments/deficits in the dimension/domain of cognition. The rationale for the selection of those individuals with at least one prior major depressive episode (MDE), is based on extant literature indicating that individuals with recurrent MDD are at greater risk of inter-episodic “non-mood” symptoms including, but not limited to, cognitive impairments (e.g., indecision, difficulties with memory, and inability to concentrate) [8–11].

Similarly, the ideal participants would be antidepressant naïve and not receiving any psychotropic medication. However, the majority of patients with MDD seeking healthcare and/or utilizing healthcare systems have been prescribed and are taking at least one psychotropic medication including, but certainly not limited to, an antidepressant. Indeed, the possibility of

introducing potential confounds moderated by medication (i.e., iatrogenic artifacts) are raised when including patients taking antidepressants and/or other psychotropic/general medications; nonetheless, excluding patients currently receiving pharmacological treatment would significantly reduce the feasibility of a timely enrollment and would be liable to criticisms of non-representativeness. Therefore, participants would be evaluated by a study clinician on a case-by-case basis to determine the potential of pharmacodynamic interactions between the study intervention and the participant's current medication regimen as well as evaluating the likelihood of impacting study results.

Participants are advised to **NOT** use the THINC-it tool outside of the study, as to not affect study results during your participation.

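### For patients who enter on an antidepressant, the default cross-taper fills about 71-100% of the Day 0-14 early-change window, and the plan has no Week 2 analysis adjusted for or split by entry use

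*Combined protocol and SAP*

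**What the plan says.** All references are to the combined protocol and SAP.

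- **Transition to Enrollment.** The existing antidepressant is reduced over 10-14 days. "At the same time, participants will be started on 10mg of Vortioxetine", and "both drugs will be co-prescribed for about 10-14 days and then the index antidepressant will be discontinued". There is an exception: should the patient's "physician determine another optimal schedule, this will be followed instead". Other psychotropic drugs stay: "Patient will discontinue only antidepressants". The section also says "Patients will be seen by a clinician on a biweekly basis for the antidepressant washout period".
- **Visit 2 (baseline), Study Medication and the MDD Patient Summary Chart.** Vortioxetine is first dispensed at Week 0 and is given at 10 mg/day on days 1-14. THINC-it is administered at Weeks 0, 2 and 8.
- **Secondary Objectives.** Week 2 THINC-it change is the predictor in both. The first concerns MADRS response (a fall of at least 50%) at endpoint. The second asks whether Week 2 change can pick up vortioxetine's effect on SDS, EWPS and WHO-5 at endpoint.
- **Eligibility Criteria.** The sponsor accepts that the possibility of "introducing potential confounds moderated by medication (i.e., iatrogenic artifacts) are raised when including patients taking antidepressants". The only response is case-by-case clinician review at entry.
- **Statistical Plan and Test Sensitivity.** The secondary objectives are to be met by correlative analysis. No covariate, stratum, subgroup or sensitivity analysis by entry antidepressant use is named. Analyses may change after an exploratory look at the data.

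**The concern.** A patient who enters without an antidepressant has a Week 2 change that reflects starting vortioxetine, practice and natural course. A patient who enters on one has all of these plus the withdrawal of another drug, over nearly the same days. Practice effects remain in both kinds of patient, since the baseline session is only meant "to work through the modified THINC-it to minimize potential practice effects". Continuing psychotropics can also remain in both. The taper is what differs between them.

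If patients who switch differ from the others in both Week 2 change and endpoint score, a correlation pooled over all MDD patients partly reflects who was switching. This matters most for the second secondary objective, which is worded in terms of a vortioxetine effect. For the first, the pooled association is a legitimate predictive target, and adjustment only shows what Week 2 change adds beyond prior drug use. The healthy controls cannot separate the two components, because they neither taper an antidepressant nor start vortioxetine.

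**Working it through.** **1. Overlap with the early-change window**

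Inputs: co-prescription of 10-14 days (Transition to Enrollment); a window from Day 0 to Day 14 (Secondary Objectives); both drugs overlapping from the first vortioxetine dose.

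Share = co-prescription days inside the window / 14.

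| Taper length | First dose Day 0 | First dose Day 1 |
|---|---|---|
| 10 days | 10/14 = 71% | 10/14 = 71% |
| 12 days | 12/14 = 86% | 12/14 = 86% |
| 14 days | 14/14 = 100% | 13/14 = 93% |

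With a Day 0 start, only 4, 2 or 0 days of the window are on vortioxetine without the old drug. This is calendar overlap in affected patients only. It is not an estimate of bias.

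**2. Could the taper come before baseline?** The section title and the washout wording might suggest so. But the taper is tied to the start of vortioxetine, and no vortioxetine is scheduled before Week 0. The default therefore falls inside the window; an individual physician's schedule may not.

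**3. What a pooled correlation could pick up (assumed links)**

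The plan gives no figure to reproduce. Let *a* be the correlation of entry use with Week 2 change and *b* its correlation with the outcome, both assumed. With no association within either group, the pooled correlation is *a* x *b*.

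- Completers: 100 x (1 - 0.20) = 80, from the 20% attrition in Recruitment. The Statistical Plan analyses only participants with complete 8-week data.
- Two-sided 5% critical |r| with 78 df: 0.220.
- On Fisher's scale the standard error is 1/sqrt(77) = 0.114, and 0.220 becomes 0.224.

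| Assumed a = b | Pooled r | Upper tail | Lower tail | False-positive rate |
|---|---|---|---|---|
| 0.2 | 0.04 | P(Z > 1.61) = 5.4% | P(Z < -2.31) = 1.0% | 6.4% |
| 0.3 | 0.09 | P(Z > 1.17) = 12.1% | P(Z < -2.75) = 0.3% | 12.4% |

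Simulation (80 patients, 50:50 split, 20,000 runs) gives the same 6.4% and 12.4%. A partial correlation given entry use holds 4.8% and 5.0%. At a 75:25 split the pooled rates are 6.2% and 12.3%.

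The gap between groups on each measure that these links require is r / sqrt(pq(1 - r^2)) SD, with p and q the group shares. At 50:50 it is 0.41 and 0.63 SD; at 75:25 it is 0.47 and 0.73 SD. Links of opposite sign would push the pooled correlation the other way and could hide a real association. The calculation suits the continuous outcomes; for MADRS response it is only indicative.

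**4. Price of adjusting**

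One degree of freedom moves the critical |r| from 0.220 to 0.221. If entry use correlates with Week 2 change at *r*, the standard error grows by 1/sqrt(1 - r^2): 1.05 at 0.3 and 1.15 at 0.5. Descriptive 95% CI half-widths for Week 2 change are 0.32 change-score SD with 40 patients and 0.47 with 20 (group sizes assumed).

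**The case against.** The best case for leaving the plan alone has four parts.

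- **The size is assumed.** No document links entry use to Week 2 change or to outcome, and none gives the share of patients entering on an antidepressant. The majority mentioned under Eligibility Criteria is for any psychotropic. At the lower link the inflation is about one percentage point. If nearly everyone enters on an antidepressant, there is little between-group difference to adjust for. All of this stands.
- **The plan names no covariates at all,** so singling out this one may look like preference. This stands only in part: it is the medication confound that the sponsor raises itself, and its default timing coincides with the predictor window. The clause allowing analyses to change is no remedy, because any adjustment would then be chosen after seeing the data.
- **A yes/no covariate is blunt.** It removes a mean shift only. It cannot separate taper from prior non-response, and it does not capture a different slope, added noise or a non-default schedule. This stands, and it limits what the adjusted result may be used for.
- **The medication record may be thin.** The screening text mentions the number of psychotropics, and the visit chart does not state drug class or taper dates. A yes/no entry variable is probably recoverable; actual taper timing may not be. The split should therefore be by entry use, not by observed cross-taper.

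A reader might also infer that the primary objective is compromised in the same way. The early-window argument does not support that: on the default schedule the taper ends by Day 14, six weeks before the Week 8 endpoint.

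**Conclusion.** The point holds for the Week 2 secondary analyses. On the default schedule the cross-taper occupies 71-100% of the early-change window (71-93% with a Day 1 start) in patients who enter on an antidepressant, and no analysis step answers the confound the sponsor acknowledges. Confounding is possible, not shown. With assumed links of 0.2-0.3 and 80 completers, the pooled false-positive rate is about 6-12% rather than 5%.

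Two stronger readings are tempting and are not supported. One is severe inflation: links of 0.5 would give about 63%, but they need a gap of about 1.15 SD on both measures at a 50:50 split (1.33 SD at 75:25), and nothing in the documents suggests this. The other is that the adjusted analysis should become the main result for the second secondary objective. All MDD patients receive open-label vortioxetine, so no covariate within that group can isolate the drug's effect.

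**What to change.** Add a few lines to the Statistical Plan:

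1. Keep the pooled Week 2 associations as planned for both secondary objectives.
2. Pre-specify a sensitivity analysis of MADRS response, SDS, EWPS and WHO-5 adjusted for antidepressant use at entry (yes/no), by partial correlation or regression (logistic for MADRS response). Take the variable from the Current Medications record at screening, updated at Day 0, when "Participant will be asked to report any adverse event(s) or any changes to medications". Confirm that the record identifies antidepressants by name or class.
3. Report Week 2 THINC-it change with 95% CIs by entry antidepressant use, as descriptive only.
4. State the reading rule in advance: if pooled and adjusted results differ, the Week 2 association is not attributed to vortioxetine. If they agree, the adjusted result is still not presented as isolating a vortioxetine effect.

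No new assessment is needed, provided that the medication record identifies antidepressants. The cost is one degree of freedom, a standard error about 5-15% larger if entry use correlates 0.3-0.5 with Week 2 change, and imprecise subgroup estimates with about 80 completers.
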